8. MEASUREMENT OF EXPOSURE TO STUDY DRUG

The total duration of exposure is defined as the time interval between the first dose and the last dose, inclusive, of study drug based on the patient study drug dosing information. In case if significant (e.g. >5%) number of subjects will switch doses during the study, additional tabulation by dose will be performed. Total duration (weeks) of exposure to study drug in the FAS population will be summarized by descriptive statistics (ie, total number, mean, standard deviation, median, minimum, and maximum) - see "Summary of study data".

Data for study patients' compliance will be summarized and tabulated by visit.

Area under curve as product of compliance for distinct period (e.g. time between visits) and duration of this period) will be calculated and summarized.

9. EFFICACY ANALYSES

The primary, secondary, and exploratory efficacy analysis will be performed in two sets of data:

- 1) Full Analysis Set (defined as enrolled subjects who tookat least one dose of study drug)
- Per protocol analysis set (defined as subjects who took at least one dose of study drug and having all inclusion and no exclusion criteria)

For performing interim analysis data of first 470 enrolled patients will be used for the efficacy analyses listed in this section. For the interim efficacy analyses applicable methodology listed in this section is planned to be used. The interim analysis will be performed on the base of full analysis set.

9.1. Statistical Analysis of the Primary Efficacy Variable(s)

Primary study outcome – change from baseline in clinic SBP value to Visit 4 will be estimated with 95% confidence interval construction and analyzed with paired t-test in pairwise comparison with baseline SBP

Changes in systolic BP (SBP) during the treatment with Edarbi[®] will be evaluated from baseline to Month 1,3 and 6. Additionally the changes of SBP from baseline to mentioned visits will be analyzed with paired T-test in pairwise comparisons with baseline level of the variable.

In addition, clinic SBP (DBP) change from baseline will be assessed and evaluated using Mixed model repeated measures (MMRM) methodology. The multiple visits for each patient will be incorporated as repeated measures within each patient. Visit will be treated as a categorical predictor and baseline SBP (DBP) will be included as a covariate. An appropriate covariance structure will be selected to provide estimates (Least Square Means) of change from Baseline and to perform statistical analysis at Visit 4 (Month 6). In addition, Least Squares Means, the associated standard errors and 95% confidence intervals will be displayed by each individual dose group (in case if exposition assessment will reveal distinct dose groups, then group factor and group * visit interaction will be added to the model).

Patients who reached target level of SBP (DBP) at visits 2, 3 and 4 will be presented using frequencies and percentages for the study population.

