7.2 Study Sites

The study is planned to be conducted in approximately 80 investigational sites from the Russian Federation and about 10 investigational sites in the Republic of Kazakhstan.

The study sites will be selected according to following criteria:

- out-patient clinics,
- availability of cardiologist specialists in out-patient clinics,
- significant patient flow with essential hypertension (the sites should treat at least 350 patients with hypertension per year).

The Sponsor/responsible CRO will keep a record of the individuals responsible for each participating Study Site, the Investigators. The chosen Investigators must have qualifications and expertise directly related to the Study.

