13.4 Determination of Sample Size

Sample size was calculated for the primary objective of the study: to estimate the effect of Edarbi® treatment on blood pressure for patients with increased weight or obesity. This estimation will be conducted with 95% confidence interval construction. Sample size was calculated using SAS 9.3 proc power procedure (Confidence Interval for Paired Mean Difference) for following parameters (fixed scenario elements):

Fixed Scenario Elements	
Distribution	Normal
Method	Exact
Alpha	0.05
CI Half-Width	1
Standard Deviation	17.79
Correlation	0.4375
Nominal Prob(Width)	0.9
Number of Sides	2

Prob Type	Conditio nal
------------------	-------------------------

Where the distribution is assumed to be normal, alpha specifies the level of significance, Nominal Prob (Width) specifies the desired probability of obtaining a confidence interval half-width less than or equal to the value specified as CI Half-Width. Half-width of the desired confidence interval was set to 1 mm Hg. Standard deviation and correlation coefficient were estimated by pooling recent studies data [12, 13, 14, 19, 20] for clinic Systolic Blood Pressure after at least 6 weeks of antihypertensive treatment with azilsartan medoxomil. Pooled effect estimation (clinic SBP difference at the end of the treatment from baseline SBP value) is -17.311 with pooled SD of 17.7887, which corresponds to the standardized difference of -0.9731 and correlation coefficient of 0.4375. For the denoted scenario, it is required to receive data from at least 1437 patients before-after the treatment.

Computed N Pairs	
Actual	N
Prob(Width)	Pairs
0.903	1437

Taking into account a possible dropout of 25%, it is recommended to enrol at least 1916 patients into the study.

According to the reference studies [24-29], the SD for effect for DBP is less than the SD for SBP, so the denoted number of patients will be sufficient for the corresponding secondary outcomes.

14 Reports

A Non-Interventional Study Report based on the results obtained will be prepared and submitted to the Sponsor for distribution. The Final Study Report should be available within one year from collection of the last data point, and the participating sites should be informed about the results when the report is finalised. Composed the study report should be provided to the IEC.

15 Publications

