5. STATISTICAL / ANALYTICAL ISSUES

Visit windows

In accordance with the protocol, due to the non-interventional study design it's not possible to appoint exact times for the study visits, although it is expected that the period of observation will be approximately 6 months. The frequency of the visits will be assigned by each physician according to their routine practice. It is anticipated that the patients will visit their physician every 3 months and more often at the beginning until the patient achieves target blood pressure.

So, for the analysis and summary of clinical laboratory, efficacy, and safety data in case of this analysis/summary performed on "by visit" base. In the event of multiple values for an assessment within an analysis window, the value closest to the scheduled visit date will be used for analyses. If two values tie as closest to the time point (for example, one value is before and the other value is after the time point), then the later value will be selected as the analysis value.

Analysis Window	Start	End	Target Asses dupli	sment to be used if cates	
Baseline visi	t <1		NA		
Month 1 Month 3 Month 6	2 46 136	45 135 NA	30 90 Closes 180 equidi	st to target day, if stant use later result.	

The definition for the study days included in each study window is defined as below:

Treatment Day prior to first dose = Visit Date – Date of First Dose

Treatment Day on or after first dose = Visit Date – Date of First Dose + 1

Adjustments for Covariates

No specific adjustments for covariates will be made in all statistical analyses, unless specified otherwise per-analysis level.

Handling of Dropouts or Missing Data

Missing efficacy outcomes will be assumed to be missing at random (MAR) and thus will not be imputed in the primary analysis. However, if greater than 1% of all primary/secondary outcomes that should be available for analysis are missing, a sensitivity analysis will be undertaken in addition to the primary MAR analysis.

Confidential

This sensitivity analysis will include an evaluation of the results of models developed under the assumptions of:

1) last observation carried forward;

2) worst extreme case imputation and;

3) regression model imputation using all available information.

Outlier identification

During data Quality Control outlier identification will be performed using adjusted Z-score method (Iglewicz and Hoaglin, 1993).

$$M_i = \frac{0.6745(x_i - \tilde{x})}{MAD}$$

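### The precision calculation and the primary confidence interval treat patients from about 90 sites as independent, so both are optimistic if SBP change is positively correlated within site

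*SAP*

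**What the plan says.** Precision is the only design target. Protocol 13.4 says of the primary objective: "This estimation will be conducted with 95% confidence interval construction". It adds: "Half-width of the desired confidence interval was set to 1 mm Hg", to be met with probability 0.9. From an SD of 17.79 and a correlation of 0.4375 it concludes that "it is required to receive data from at least 1437 patients before-after the treatment". A 25% dropout allowance takes this to 1916 enrolled. The listed inputs contain no design effect or ICC.

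Protocol 7.2 plans "approximately 80 investigational sites from the Russian Federation and about 10 investigational sites in the Republic of Kazakhstan".

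For the primary outcome, Protocol 13.2.2 plans a 95% confidence interval and names no site term or standard-error method. SAP 9.1 says that the change "will be estimated with 95% confidence interval construction and analyzed with paired t-test in pairwise comparison with baseline SBP". SAP 2.4 and SAP 4 restrict that SAP's analysis to the Kazakhstan data, and SAP 2.4 notes that no sample size was calculated for that subgroup. In both documents the additional MMRM models visits within patient, with no effect for site.

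SAP 5 states: "No specific adjustments for covariates will be made in all statistical analyses", with an exception where an individual analysis says otherwise. Site otherwise appears only in the sort order of listings (Protocol 13.2.1, SAP 3) and in a tabulation of doses by region of site location (SAP 9.3.1).

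**The concern.** Patients at one site share things that can move the primary outcome. Protocol 9.2 leaves care decisions to the participating physicians, Protocol 9.5 lets each physician set the visit frequency, and Protocol 10.7 ties examinations to the routine of the particular institution. The choice between monotherapy and combination therapy is also the physician's. It is therefore plausible, though not shown in the documents, that SBP changes within a site are more alike than changes between sites.

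If so, 1437 evaluable patients carry less information than 1437 independent ones. A standard error that ignores site is then too small, the reported 95% interval covers less than 95%, and the one quantity the study was sized to deliver is overstated. Kazakhstan has the same problem with only about 10 sites, where the between-site variance is estimated from very few units.

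**Working it through.** **Inputs.** From Protocol 13.4: alpha 0.05 two-sided, half-width 1, SD 17.79, correlation 0.4375, probability 0.9 (conditional), 25% dropout. From Protocol 7.2: about 80 + 10 = 90 sites. Assumed, not in the documents: ICC of 0.01 to 0.10, and equal site sizes unless stated.

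**Reproducing the plan's figure.** SD of the paired difference = 17.79 × √(2 × (1 − 0.4375)) = 18.87. The smallest n whose half-width is at most 1 with conditional probability 0.9 is 1437, with actual probability 0.9027 (stated: 0.903). 1437 / 0.75 = 1916. Both figures reproduce exactly, so no clustering allowance is hidden in them.

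**Which SD.** Protocol 13.4 also describes the pooled effect as a difference from baseline "with pooled SD of 17.7887, which corresponds to the standardized difference of -0.9731 and correlation coefficient of 0.4375". Indeed −17.311 / 17.7887 = −0.9731, so 17.79 can be read as already the SD of change. Both readings are carried below.

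**Half-width with independent patients.** 1.962 × 18.87 / √1437 = 0.976 mm Hg. With 17.79 it is 1.96 × 17.79 / √1437 = 0.92 mm Hg.

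**Clustering.** Mean evaluable patients per site m = 1437 / 90 = 15.97. Design effect DE = 1 + (m − 1) × ICC. Correct half-width = independent half-width × √DE. Actual coverage of the uncorrected interval = 2Φ(1.96 / √DE) − 1. Effective n = 1437 / DE.

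| Assumed ICC | DE | Effective n | Actual coverage | Half-width, SD 18.87 | Half-width, SD 17.79 |
|---|---|---|---|---|---|
| 0 | 1.00 | 1437 | 95.0% | 0.98 | 0.92 |
| 0.01 | 1.15 | 1250 | 93.2% | 1.05 | 0.99 |
| 0.02 | 1.30 | 1106 | 91.5% | 1.11 | 1.05 |
| 0.05 | 1.75 | 822 | 86.2% | 1.29 | 1.22 |
| 0.10 | 2.50 | 576 | 78.5% | 1.54 | 1.45 |

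**Where 1 mm Hg is passed.** ICC = ((1 / 0.976)² − 1) / 14.97 ≈ 0.003 with SD 18.87, and ((1 / 0.92)² − 1) / 14.97 ≈ 0.012 with SD 17.79.

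**Sensitivity (SD 18.87).**
- Unequal sites: DE = 1 + ((1 + CV²)m − 1) × ICC. With an assumed CV of 0.8 and ICC 0.05, the half-width is 1.47 mm Hg and coverage 80.8%.
- No dropout: with all 1916 evaluable (21.3 per site), the half-width is 0.93 / 1.00 / 1.20 / 1.47 mm Hg for ICC 0.01 / 0.02 / 0.05 / 0.10. Coverage is then 92.6 / 90.2 / 83.3 / 74.0%, because the sites are larger.

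**Kazakhstan.** No N is planned. A proportional share of 1437 × 10 / 90 ≈ 160 evaluable patients at 10 sites is assumed, with SD 18.87. The uncorrected half-width is 2.95 mm Hg. With the design effect and a t reference on 9 df (2.262) it is 3.62 / 3.85 / 4.46 / 5.34 mm Hg for ICC 0.01 / 0.02 / 0.05 / 0.10. Part of this comes from the degrees of freedom alone: at ICC 0 on 9 df it is 3.38.

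**The case against.** The strongest reply is that the problem is conditional and its size unknown. The documents give no ICC, and at 0.01 the half-width is 1.05 or 0.99 mm Hg, depending on the SD. A constant measurement offset at a site cancels in a change from baseline, so local measuring habits alone need not create correlation. If the target is the mean change at these particular sites, chosen by criteria and not sampled, between-site variance need not enter. No success criterion depends on the 1 mm Hg, and Protocol 13.2.4 already concedes that an uncontrolled study cannot fully evaluate efficacy. All of this stands as a limit on the size of the point. It does not remove it: shared treatment and visit routines act on the change itself, and the proposed method estimates the correlation from the data and widens the interval little if it is near zero.

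Some stronger inferences are tempting and are not supported:

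- **That the SAP 9.1 sentence shows the analysis of 1437 patients at 90 sites.** It governs the Kazakhstan data. For the whole study, Protocol 13.4 documents the independence assumption outright. Protocol 13.2.2 merely names no site term, and a reader cannot tell whether another document adds one.
- **That any within-site correlation makes the interval too narrow.** It must be positive.
- **That the 1 mm Hg target will certainly be missed.** This depends on the ICC, on which SD applies, and on how many patients are evaluable.
- **That SAP 5 rules out clustered standard errors.** It concerns covariate adjustment, not variance estimation, and it allows exceptions.

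For Kazakhstan, SAP 2.4, 3 and 5 already warn of the limited sample. That warning concerns sample size and does not correct the interval.

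**Conclusion.** The point holds in conditional form. The stated precision assumes zero within-site correlation, and nothing in either document allows for anything else. If the ICC of SBP change is positive and the result is meant to apply beyond the participating sites, the primary interval is too narrow. Over an assumed ICC of 0.01 to 0.10, actual coverage falls from 93.2% to 78.5%. The half-width rises from 1.05 to 1.54 mm Hg (SD of change 18.87) or from 0.99 to 1.45 mm Hg (SD 17.79). The effect is small at the low end and material from about 0.05.

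A reader might go further and infer that the efficacy estimate or its significance is in doubt. It is not. Clustering does not bias the mean change, and with a planning value of −17.3 mm Hg, half-widths of this order leave the test against zero unchanged. What is affected is the claimed precision and the coverage of the interval.

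**What to change.** **Primary interval.** Compute the interval for SBP change, and the one for DBP, with a standard error clustered by site and a t reference on sites − 1 df. Alternatively, take it from a model of the change with a random site intercept. The clustered standard error leaves the planned point estimate as it is; the mixed model reweights sites of unequal size. A random site intercept added only to the supportive MMRM would not correct the primary interval.

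**Kazakhstan.** With about 10 sites a plain sandwich estimator tends to be too small. Use a bias-corrected version on 9 df, or the random-intercept model with a small-sample correction such as Kenward-Roger. Under the assumptions above, expect a half-width of about 3.6 to 5.3 mm Hg.

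**Protocol 13.4.** State that the 1 mm Hg half-width assumes zero within-site correlation, give the half-widths for ICC 0.01 to 0.10, and say whether 17.79 is the SD of a single measurement or of the change. Report the estimated ICC with the results.

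**Cost.** Some SAP wording and a small change to the analysis code, with more care needed for Kazakhstan. No new data, visits or patients are required. The downside is a somewhat wider interval.

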9.2 Statistical Analysis of the Secondary Efficacy Variables

Secondary and exploratory outcomes will be analyzed using descriptive statistics and frequencies and percentages as follows:

- Changes in diastolic BP (DBP) during the treatment with Edarbi[®] (from baseline to Month 1, Month 3, Month 6) will be calculated and presented in summary tables using descriptive statistics for continuous variables for overall population of analysis and in subgroups of patients listed in the section 9.3. Additionally the changes of this variable in the population and mentioned subgroups will be analyzed with paired T-test in pairwise comparisons with baseline level of the variable.
- Percentage of patients who achieve target SBP<140 mm Hg (at Month 1, Month 3, Month 6) will be described and presented in summary tables using absolute frequencies and percentages as well as 95% confidence intervals,

- Percentage of patients who achieve target DBP<90 mm Hg (at Month 1, Month 3, Month 6) will be described and presented in summary tables using absolute frequencies and percentages as well as 95% confidence intervals;
- Percentage of patients who respond to Edarbi[®] therapy (defined as decrease of SBP≥ 20 mm Hg or decrease of DBP≥10 mm Hg; Month 1, Month 3, Month 6) will be described and presented in summary tables using absolute frequencies and percentages as well as 95% confidence intervals;
- Percentage of patients who achieve target BP (defined as SBP<140 mm Hg, DBP<90 mm Hg; at Month 1, Month 3, Month 6) will be described and presented in summary tables using absolute frequencies and percentages as well as 95% confidence intervals;
- 6. Descriptive characteristics of patients before the start of Edarbi[®] therapy: age, gender, HTN stage and grade, Baseline SBP and DBP; BMI, previous therapy of HTN, risk factors, % of patients with diabetes mellitus, % of patients with metabolic syndrome; target organ damage by HTN, eGFR, comorbidities; type of antihypertensive therapy initiated at baseline (monotherapy; double therapy; triple therapy; other (>3)); distribution of classes of antihypertensive drugs used in combination therapy with a distribution of INNs used. The information will be presented in summary tables
- Changes in serum creatinine, eGFR (CKD-EPI), urea, total cholesterol, triglycerides, low density lipoproteins, high density lipoproteins (from baseline to Month 1- Month 3- Month 6) will be assessed and presented in summary tables using descriptive statistics for continuous variables. Additionally the changes of this variable will be analyzed with paired T-test in pairwise comparisons with baseline level of the variable.
- Changes of blood glucose level, glycated hemoglobin (HbA1c) from baseline to the visits 2, 3, and 4. For the analysis 95% Cis will be constructed. Additionally the changes of this variable will be analyzed with paired T-test in pairwise comparisons with baseline level of the variable.

9.0 Analysis of BMI and waist circumference change from baseline to visit 4. 95% CIs will be constructed. Additionally the changes of this variable will be analyzed with paired T-test in pairwise comparisons with baseline level of the variable.

10. Reasons for discontinuation of Edarbi[®] therapy will be described and presented in summary tables using absolute frequencies and percentages as well as 95% confidence intervals.

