5. Is currently participating in a clinical trial. Participation in non-interventional registries is permitted.
6. Vulnerable patients who are unable to understand information about study or those who depend on investigator.

Duration of data collection per patient

Data collection per patient will be carried out within the framework of the routine practice. Due to the non-interventional study design it's not possible to appoint exact times for the study visits, although it is expected that the period of observation will be approximately 6 months. The frequency of the visits will be assigned by each physician according to their routine practice. It is anticipated that the patients will visit their physician every 3 months and more often at the beginning until the patient achieves target blood pressure. Information for the study will be collected from 4 patients' visits to the physician.

Criteria for evaluation

Population descriptors

The main variables, which will be collected in the study, are presented in the table.

Variables collected	Baseline visit (V1)	Observational visit 1 (V2)	Observational visit 2 (V3)	Final visit (V4)
Demographic information	X			
Medical history (incl. risk factors, prior diseases, prior HTN therapy etc)	X			
Physical examination and vital signs*	X	X	X	X
HTN therapy (drugs, doses)	X	X	X	X
Laboratory tests and instrumental exams*	X	X	X	X
Concomitant medication	X	X	X	X
Adverse events	X	X	X	X

* All examinations (physical examination and vital signs, laboratory tests and instrumental exams) are done in accordance with clinical routine practice and physician's decision. Instrumental exams are measurement of blood pressure, heart rate, ECG, 24-hour ambulatory blood pressure monitoring. All examinations should be registered in the CRF only if they are done in routine practice.

Primary outcomes:

- Change from baseline in clinic SBP on Edarbi® therapy (Time Frame: Baseline and V4)

Secondary outcomes:

- Change from baseline in clinic DBP on Edarbi® therapy (Time Frame: Baseline and V4);
- Proportion (%) of patients who respond to Edarbi® therapy (defined as decrease of SBP \geq 20 mm Hg or decrease of DBP \geq 10 mm Hg; Time Frame: Baseline and V4);
- Proportion (%) of patients who achieve target SBP <140 mm Hg (Time Frame: Baseline and V4);
- Changes from baseline in clinic SBP in subgroups of patients: BMI (overweight, obese), impaired glucose tolerance, metabolic syndrome, diabetes mellitus (Time Frame: Baseline and V4);

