9.4.1 Criteria inclusion

Every eligible patient at participating investigational sites must meet the following criteria:

1. Male and female patients ≥ 18 years of age with HTN 1-2 grade*
2. Patients with:
 - Newly diagnosed arterial HTN or
 - inadequately controlled previously prescribed monotherapy with RAAS blocker or
 - inadequately controlled previously prescribed combination therapy with RAAS blocker + diuretic or RAAS blocker + calcium antagonist.
3. The physician decides to prescribe Edarbi®
 - as monotherapy or
 - as a part of combination therapy including diuretics or calcium antagonists;
4. Overweight or obesity of any degree (body mass index $> 25 \text{ kg/m}^2$);
5. Is capable of understanding the written informed consent, provides signed and written informed consent, and agrees to comply with protocol requirements. In case the patient is blind or unable to read, informed consent will also be witnessed.

* in accordance with guidelines of the Russian Ministry of Health for the management of HTN [6] and Kazakh protocol on clinical diagnosis and treatment of hypertension (2013) [7].

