13.2.2. Statistical analysis methods

Primary study outcome – change from baseline in clinic SBP value tot Visit 4 will be estimated with 95% confidence interval construction.

In addition, clinic SBP (DBP) change from baseline will be assessed and evaluated using Mixed model repeated measures (MMRM) methodology [30, 31]. The multiple visits for each patient will be incorporated as repeated measures within each patient. Visit will be treated as a categorical predictor and baseline SBP (DBP) will be included as a covariate. An appropriate covariance structure will be selected to provide estimates (Least Square Means) of change from Baseline and to perform statistical analysis at Visit 4. The dose-response trend hypothesis test will be conducted using the appropriate contrast statement for a linear (ordinal dose) trend. In addition, Least Squares Means, the associated standard errors and 95% confidence intervals will be displayed by each individual dose group.

Patients who reached target level of SBP (DBP) at visits 2, 3 and 4 will be presented using frequencies and percentages for the study population. Patients who respond to therapy at visits 2, 3 and 4 will also be presented using frequencies and percentages. Secondary and exploratory outcomes will be analysed using descriptive statistics and frequencies and percentages as follows:

- Changes in systolic BP (SBP) during the treatment with Edarbi® (V2-V3) will be calculated and presented in summary tables using descriptive statistics for continuous variables;
- Changes in diastolic BP (DBP) during the treatment with Edarbi® (V2, V3) will be calculated and presented in summary tables using descriptive statistics for continuous variables;
- Percentage of patients who achieve target SBP<140 mm Hg (V2, V3, V4) will be described and presented in summary tables using absolute frequencies and percentages as well as 95% confidence intervals,
- Percentage of patients who achieve target DBP<90 mm Hg (V2, V3, V4) will be described and presented in summary tables using absolute frequencies and percentages as well as 95% confidence intervals;
- Percentage of patients who respond to Edarbi® therapy (defined as decrease of SBP \geq 20 mm Hg or decrease of DBP \geq 10 mm Hg; V2, V3, V4) will be described and presented in summary tables using absolute frequencies and percentages as well as 95% confidence intervals;

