2.4 Sample size and power

This particular analysis is performed for the subgroup of study participants from Republic of Kazakhstan. There was no formal power or sample size calculation planned in the protocol for this subgroup, only the total sample size (taking Russian Federation and Republic of Kazakhstan as one sample for analysis). Therefore, certain results may be unavailable or not applicable due to the small sample size of subgroup from Republic of Kazakhstan.

3. DATA ANALYSIS CONSIDERATIONS Overall analysis frame

This study is observational and epidemiological methods will be employed for data analyses. Descriptive analysis will be performed of all collected data, i.e. all data listed in section 2.3 ("Study variables"), except for the data collected only for the purpose of data cleaning.

The primary and secondary outcomes of the study are presented in section 2.3.1 ("Efficacy variables").

Summary of study data

All continuous variables will be summarized using the following descriptive statistics: n (nonmissing sample size), mean, standard deviation, median, 25 percentile, 75 percentile, maximum and minimum. The frequency and percentages (based on the non-missing sample size) of observed levels will be reported for all categorical measures. For variables marked "binary" exact (Clopper-Pearson) 95% confidence intervals will be calculated where appropriate. For categorical variables with more than 2 categories 95% confidence intervals will be calculated using Goodman's method or other appropriate (e.g. Sison and Glatz) method.

In general, all data will be listed, sorted by site and patient, and when appropriate by visit number within patient. All summary tables will be structured with a column for each cohort in the increasing order and will be annotated with the total population size relevant to that table/dose cohort, including any missing observations.

Baseline data

The baseline visit is defined as the last observations collected prior to administration of the study drug.

Analysis of data from republic of Kazakhstan

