9.3 Additional methods of analysis

9.3.1 Subgroup analyses. Primary efficacy variable as well as the variables listed at the items 1-10 in the section 9.2 will be analyzed both in general population and in the following subgroups (if applicable):

- patient sex (male/female);
- patient age (60 or more, <60 years old);
- BMI (normal (<25); overweight (25-30), obese (>30_) and according to grade of obesity (grade I 30-34,9; Grade II 35-39,9; Grade III ≥40)
- metabolic syndrome (yes, no),
- diabetes mellitus (yes, no),
- diabetes mellitus, impaired glucose tolerance or normal glucose metabolism
- subgroups with different eGFR according to CKD-EPI (eGFR <30; 30-59 and >=60);
- subgroups according to previous antihypertensive treatment (treated/not treated and treated patients according to class of antihypertensive treatment used before initiation of Edarbi); the group of patients who was treated with RAAS blocker monotherapy and the group of patients who was treated with combination of RAAS blocker and diuretic and the group of patients who was treated with RAAS blocker and Calcium channel blocker to be described separately.
- patients with newly diagnosed hypertension
- The subgroup of patients with isolated systolic hypertension (patients not treated with antihypertensive treatment before the study who has SBP ≥140 mm Hg and DBP <90 mmHg at visit 1).
- diabetes mellitus or metabolic syndrome or nothing;
- Subgroup of Patients with Chronic heart failure and patients without chronic heart failure in diagnosis
- Subgroups according to risk factors: smokers/non-smokers; family history of cardiovascular disease (yes/no)
- Subgroups according to target organ damage by HTN (yes/no; if yes according to organs involved (heart, kidney, brain, eyes, vessels).

- Subgroups according to antihypertensive treatment initiated at baseline level: monotherapy with azilsartan and patients receiving combination therapy with azilsartan (both in general and according to type of used combination (double therapy; triple therapy, other) and per classes of used in combination))

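### The DBP<90 and SBP<140 rates are control rates at a visit; labelled as target 'achieved' on Edarbi, they mix patients already below the limit at Visit 1 with those who newly reach it

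*SAP*

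**What the plan says.** **The rates.** SAP 9.2 lists the "Percentage of patients who achieve target DBP<90 mm Hg (at Month 1, Month 3, Month 6") and the "Percentage of patients who achieve target SBP<140 mm Hg (at Month 1, Month 3, Month 6"), each with a 95% confidence interval. Protocol 13.2.2 has the same pair, for example "Percentage of patients who achieve target DBP<90 mm Hg (V2, V3, V4"). SAP 9.1 also tabulates patients who reached the SBP (DBP) target at visits 2, 3 and 4. None of these texts sets a condition on the Visit 1 value.

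**The denominator.** SAP section 3 (Summary of study data) states: "The frequency and percentages (based on the non-missing sample size) of observed levels will be reported for all categorical measures". The main efficacy set is the "Full Analysis Set (defined as enrolled subjects who tookat least one dose of study drug").

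**Entry.** Protocol 9.4.1 asks for "Male and female patients ≥ 18 years of age with HTN 1-2 grade". It gives no separate floor for SBP and DBP, and pre-treated patients qualify as inadequately controlled without a numeric limit.

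**Patients below 90 at entry.** SAP 9.3.1 defines an isolated systolic subgroup of previously untreated patients "who has SBP ≥140 mm Hg and DBP <90 mmHg at visit 1". It runs the section 9.2 items in its subgroups where applicable.

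**Time frame.** The secondary outcomes in protocol section 2 include the "Proportion (%) of patients who achieve target SBP <140 mm Hg (Time Frame: Baseline and V4"). Protocol 6.2 and SAP 2.3.1 give the composite target (SBP<140 and DBP<90) a time frame that also includes baseline. The analysis sections list follow-up visits only.

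**The concern.** The study has no control arm (protocol 9.3), so Visit 1 is the only reference for what happened on treatment. A rate described as achieving target invites the reader to credit the drug with every patient counted. A patient whose DBP was below 90 before the first dose and has not moved is counted in the same way as one who came down from above 90.

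Two uses of the rates are at stake. The first is the overall statement of how many patients reached a DBP or SBP target on Edarbi. The second is the subgroup tables in SAP 9.3.1. Groups defined by age, diabetes or obesity class may differ in how many patients had one normal component at entry, and the rates would then differ for that reason alone.

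**Working it through.** **The plan's own figures.** No figure is stated for the target rates. The only computed figure in the plan is the sample size: 1437 pairs, inflated to 1437/0.75 = 1916. It reproduces and does not bear on this point.

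**Inputs.** The definition, denominator, analysis set and entry rule are as set out above. Three quantities are needed that the documents do not give:

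- q: share of patients below the limit at Visit 1, assumed 10% to 50%
- s: share of those still below at follow-up, assumed 85% to 95%
- c: share of the remaining patients who are below at follow-up, assumed 50% to 70%

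**Formula.** The planned rate is R = q·s + (1 − q)·c. The rate among patients who could newly reach the limit is c. The gap is R − c = q(s − c), which is positive whenever s > c.

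**No-change check.** If nobody's blood pressure moved, then s = 1, c = 0 and R = q. The plan would report the Visit 1 share as an achievement rate. In the isolated systolic subgroup q = 1, so R = 100%.

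**Worked example.** With q = 30%, s = 90%, c = 60%: R = 0.30 × 0.90 + 0.70 × 0.60 = 0.27 + 0.42 = 69%, against 60% among those who could convert. The gap is 9 points.

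**Varying q, with s = 90% and c = 60%:**

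| q | R | R − c |
|---|---|---|
| 10% | 63% | 3 points |
| 20% | 66% | 6 points |
| 30% | 69% | 9 points |
| 40% | 72% | 12 points |
| 50% | 75% | 15 points |

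**Extremes of the assumed ranges.** Smallest gap: 0.10 × (0.85 − 0.70) = 1.5 points. Largest gap: 0.50 × (0.95 − 0.50) = 22.5 points.

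**Subgroup comparison.** Two subgroups with identical s = 90% and c = 60%, but q = 10% and q = 40%, would show 63% and 72%. That 9-point difference comes entirely from entry values.

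**Isolated systolic subgroup.** Here q = 100%, so R = s. The group at or above 90 at Visit 1 is empty, so no rate of newly reaching DBP<90 exists.

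**Composite target.** Patients in the isolated systolic subgroup have SBP of at least 140 at Visit 1. They are therefore not at SBP<140 and DBP<90 before treatment and do not enter the composite count by this route.

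**The case against.** A reader might infer that the planned rates are inflated or wrong. The documents do not support that. The share of patients below a threshold at a visit is an ordinary control rate, correctly computed for what it is. The gap worked out above is a difference between two measures, not an error in one of them. What is open to criticism is the label and the missing Visit 1 value.

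A reader might also infer that the SAP requires a meaningless DBP analysis in the isolated systolic subgroup. It does not. SAP 9.3.1 runs the items only where applicable, so the analyst may omit this one, and if run it would still show how many patients stay below 90. The qualifier does leave the choice to judgement after the data are seen.

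The plan is not silent on baseline either. Item 6 of SAP 9.2 reports baseline SBP and DBP and hypertension grade, and SAP 9.3.1 extends this to subgroups. A reader would therefore see that mean DBP differs between groups. But mock Table 2 in SAP section 11 gives continuous summaries, not the share below a limit or the number who crossed it.

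The SBP half has thinner support. It rests on the absence of an SBP floor; no subgroup with SBP<140 at Visit 1 is named.

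Finally, the rate among patients above the limit is not a clean measure of drug effect. Selecting on a high Visit 1 reading without a control arm brings in regression to the mean. That stands, and is why the restricted rate should be added beside the all-patient rate, not replace it.

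**Conclusion.** The point holds as a minor one about labelling and presentation. The component rates describe control at a visit. They do not describe achievement on Edarbi, because they combine patients already below the limit with patients who newly reach it. For DBP the SAP's own subgroup definition shows this directly; for SBP it is inferred.

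The direction needs only s > c. The size cannot be taken from the documents: about 1.5 to 22.5 percentage points is the span over assumed values of q, s and c, and no single figure within it should be read as an estimate.

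Nothing here touches the primary outcome, the change in SBP. The composite target is much less affected, and the component rates are descriptive.

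**What to change.** In SAP 9.2, with a matching edit in protocol 13.2.2:

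1. Keep the all-patient rates, but call them control at the visit.
2. Show the share below each limit at Visit 1 beside Months 1, 3 and 6. This follows the time frame that the outcome lists already give for target SBP and for the composite.
3. Add the rate among patients at or above the limit at Visit 1, with its denominator and exact 95% CI, and note that it is subject to regression to the mean.
4. State that the DBP<90 'achieved' item is not applicable in the isolated systolic subgroup.

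Before 'at or above the limit' is coded, reconcile the limits. SAP 9.2 and protocol 13.2.2 use DBP<90 for everyone, while protocol 4.2 and SAP section 3 define target DBP as <85 in diabetes. A diabetic patient with a DBP of 85 to 89 at Visit 1 is above one limit and below the other.

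The cost is a few sentences, one extra column and one extra row. Visit 1 blood pressure is already collected, so no new data are needed. The restricted rates will have smaller denominators and will probably look less favourable than the all-patient rates.
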